| 7.1 DATA COLLECTION AND MANAGEMENT | 12 |
| 7.2 CONFIDENTIALITY | 12 |
| 7.3 REGULATORY AND ETHICAL CONSIDERATIONS | 13 |
| 7.3.1 Risk Assessment, General Considerations | 13 |
| 7.3.2 Psychological Harms | 13 |
| 7.3.3 Discrimination | 13 |

| | | |
|----------|--|-----------|
| 7.3.4 | Confidentiality of Medical Information and Samples | 13 |
| 7.3.5 | Potential Benefits | 13 |
| 7.3.6 | Risk-Benefit Assessment | 13 |
| 7.4 | RECRUITMENT STRATEGY..... | 13 |
| 7.5 | INFORMED CONSENT/ASSENT AND HIPAA AUTHORIZATION..... | 14 |
| 7.5.1 | Short Form Consent Process Requiring Telephonic Interpretation Services | 15 |
| 7.5.2 | HIPAA Attestation for the Use of Decedent PHI | 15 |
| 7.6 | PAYMENT TO SUBJECTS/FAMILIES..... | 15 |
| 8 | PUBLICATION | 16 |
| 9 | REFERENCES | 17 |

ABBREVIATIONS AND DEFINITIONS OF TERMS

| | |
|-------|---|
| ADEM | Acute Disseminated Encephalomyelitis |
| CLIA | Clinical Laboratory Improvement Amendments |
| DUA | Data Use Agreement |
| HIPAA | Health Insurance Portability and Accountability Act |
| ICSL | Illumina Clinical Services Laboratory |
| IRB | Institutional Review Board |
| MDBP | Myelin Disorders Biorepository Project |
| MRI | Magnetic Resonance Imaging |
| NGS | Next Generation Sequencing |
| PHI | Protected Health Information |
| PI | Principal Investigator |
| SAE | Serious Adverse Event |
| SoC | Standard of Care |
| VUS | Variant of Unknown Significance |
| WES | Whole Exome Sequencing |
| WGS | Whole Genome Sequencing |

ABSTRACT

Context/Background:

Leukodystrophies, and other heritable disorders of the white matter of the brain, were previously resistant to genetic characterization, largely due to the extreme genetic heterogeneity of molecular causes. While recent work has demonstrated that whole genome sequencing (WGS) has the potential to dramatically increase diagnostic efficiency, significant questions remain around the impact on downstream clinical management approaches versus standard diagnostic approaches.

Objectives: (Primary and Important Secondary Objectives)

Primary

- Estimate the percentage of cases that experience a significant change in diagnostic status as a direct consequence of whole genome sequencing.

Secondary

- Estimate the percentage of cases that experience a significant change in downstream clinical management as a direct consequence of a diagnostic result through whole genome sequencing.

Study Design:

Observational study predicated on positive findings of a randomized crossover study, which demonstrated superior diagnostic efficacy of WGS compared to standard diagnostic testing.

Setting/Participants:

This is a single-site study located at the Children's Hospital of Philadelphia (CHOP). Study recruitment will continue until 100 trios (or duos) have been enrolled.

Study Interventions and Measures:

This is an observational study of subjects who are expected to receive CLIA-certified whole genome sequencing as part of their clinical care. Research-only measures will include both retrospective and prospective review of medical records.

Main Study Outcome Measures:

Clinical utility outcomes will be assessed using medical record review.

1 BACKGROUND INFORMATION AND RATIONALE

1.1 Introduction

Leukodystrophies are a group of approximately 30 genetic diseases that primarily affect the white matter of the brain^{1,2}, a complex structure composed of axons sheathed in myelin, a glial cell-derived lipid-rich membrane¹. Leukodystrophies are frequently characterized by early onset, spasticity and developmental delay, and are degenerative in nature¹. As a whole,

leukodystrophies are relatively common (approximately 1 in 7000 births or almost twice as prevalent as Prader-Willi Syndrome, which has been far more extensively studied) with high associated health-care costs; however, more than half of the suspected leukodystrophies do not have a definitive diagnosis^{3,4}, and are generally classified as “leukodystrophies of unknown etiology”. Even when a diagnosis is achieved, the diagnostic process lasts an average of eight years⁵ and results in test expenses in excess of \$8,000 on average per patient, including the majority of patients who never achieve a diagnosis at all^{6,7}. These diagnostic challenges represent an urgent and unresolved gap in knowledge and disease characterization, as obtaining a definitive diagnosis is of paramount importance for leukodystrophy patients⁸. The diagnostic workup begins with findings on cranial Magnetic Resonance Imaging (MRI) followed by sequential targeted genetic testing¹, however next generation sequencing (NGS) technologies offer the promise of rapid and more cost effective approaches.

NGS technologies have the potential to revolutionize the diagnostic process for rare diseases, especially those such as the leukodystrophies, which have seen such historically low rates of diagnosis. Our international working group (spearheaded by Drs. [name], [name], [name], [name], [name], and [name]) has extensive and globally recognized expertise in deciphering the genetics underlying unsolved leukodystrophies. They collectively have been the largest contributor to the modern understanding of leukodystrophy etiology and pathobiology. This body of work over the last decades includes the description of Vanishing White Matter Disease (*EIF2B1-5*)¹⁸⁻²⁰, 4H syndrome (*POL3RA and B*)²¹⁻²³, Leukoencephalopathy with Brainstem and Spinal Cord Involvement and Lactate Elevation (*DARS2*)^{24,25}, Megalencephalic Leukoencephalopathy with subcortical Cysts (*MLC1 and HEPACAM*)^{26,27}, Leukoencephalopathy with Thalamic involvement and Lactate and Slow Improvement (*EARS2*)^{28,29}.

In the last several years, the pace of discovery has increased at a remarkable rate due to the use of whole genome sequencing (WGS) and whole exome sequencing (WES). This includes the discovery of a novel leukodystrophy, Hypomyelination with Brain Stem and Spinal Cord Involvement and Leg Spasticity (HBSL), which is caused by mutations in *DARS*³⁰, as well as the discovery that Hypomyelination with Atrophy of the Basal Ganglia and Cerebellum (H-ABC) is caused by *de novo* *TUBB4A* mutations³¹. Finally, our group has performed the first cohort analysis of WES in leukodystrophy, with a diagnostic efficacy in the unsolved patients of nearly 50%, decreasing the overall proportion of unsolved leukodystrophy cases from 50% to approximately 25%.

Despite these advances in diagnostic efficacy, there are still significant issues with respect to implementation of NGS in clinical settings. First, sample cohorts demonstrating diagnostic efficacy are generally small, retrospective, and susceptible to ascertainment bias, ultimately rendering them poor candidates for utility analyses (to determine how efficient a test is at producing a diagnosis). Second, historic sample cohorts have not been examined prospectively for information about impact on clinical management (whether the test results in different clinical monitoring, a change in medications, or alternate clinical interventions).

To address these issues, the study team conducted an investigation of patients with suspected leukodystrophies or other genetic disorders affecting the white matter of the brain at the time of initial confirmation of MRI abnormalities, with prospective collection of patients randomly received on a “first come, first served” basis from a network of expert

clinical sites. Subjects were randomized to receive early (1 month) or late (6 months) WGS, with Standard of Care (SoC) clinical analyses conducted alongside WGS testing. An interim analysis performed in May 2018 assessed these study outcomes for a cohort of thirty-four (34) enrolled subjects. Two of these subjects were resolved before complete enrollment and were retained as controls. Nine subjects were stratified to the Immediate Arm, of which 5 (55.6%) were resolved by WGS and 4 (44.4%) were persistently unresolved. Of the 23 subjects randomized to the Delayed Arm, 14 (60.9%) were resolved by WGS and 5 (21.7%) by SoC, while the remaining 4 (17.4%) remained undiagnosed. The diagnostic efficacy of WGS in both arms was significant relative to SoC ($p<0.005$). The time to diagnosis was significantly shorter in the immediate WGS group ($p<0.05$). The overall diagnostic efficacy of the combination of WGS and SoC approaches was 26/34 (76.5%; 95% CI = 58.8% to 89.3%) over <4 months, greater than historical norms of <50% over more than 5 years.

1.2 Rationale for Approach

We anticipate that whole genome sequencing will produce measurable downstream changes in diagnostic status and clinical management, as defined by disease-specific screening for complications or implementation of disease-specific therapeutic approaches.

1.3 Compliance Statement

This study will be conducted in full accordance with all applicable Children's Hospital of Philadelphia Research (CHOP) Policies and Procedures and all applicable Federal and state laws and regulations, including 45 CFR 46, and the HIPAA Privacy Rule. Any episode of noncompliance will be documented.

The investigators will perform the study in accordance with this protocol, will obtain consent and assent, and will report unanticipated problems involving risks to research subjects or others. Collection, recording, and reporting of data will be accurate and will ensure the privacy, health, and welfare of research subjects during and after the study.

2 STUDY OBJECTIVES

This study seeks to determine whether WGS results in changes to diagnostic status and clinical management in subjects affected by undiagnosed genetic disorders of the white matter of the brain.

2.1 Primary Objective (or Aim 1)

Estimate the percentage of cases that experience a significant change in diagnostic status as a direct consequence of whole genome sequencing.

The primary objective of this study is to evaluate changes in diagnostic status in the study cohort for patients who received WGS as part of clinical care. Differences in diagnostic status will be measured at disclosure of initial results or disclosure of reanalyzed results.

Types of change in management are defined in Section 5.1.4.

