2.2 Secondary Objective (or Aim 2)

Estimate the percentage of cases that experience a significant change in downstream clinical management as a direct consequence of a diagnosis through whole genome sequencing (subjects with a diagnostic result).

The secondary objective of this study is to evaluate changes in clinical care in subjects who received a diagnosis through WGS. Differences in clinical care will be evaluated 1 year following disclosure of results.

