3.1.2 Follow-Up Period (12 Months FOLLOWING REPORT)

Subjects enrolled in the study will concurrently undergo WGS as part of their clinical care, with samples sent to the Illumina Clinical Services Laboratory (ICSL) for clinically-validated testing.

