3.2 Study Duration, Enrollment and Number of Sites

3.2.1 Duration of Study Participation

Study participation will last for 12 months following the disclosure of results.

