4 STUDY EVALUATIONS AND MEASUREMENTS

4.1 Study Outcome Measures

4.1.1 Prospective Collection of Clinical Utility Data

Clinical utility outcomes will be assessed using a combination of medical record review 1 year prior to (retrospective) and 1 year following (prospective) disclosure of results. An appropriately trained member of the study team will review this data for documented changes in care and clinical state, included changes in medical morbidities, surgeries, pharmacologic management of complications and implementation of disease specific therapies. The following data elements will be abstracted from patient medical records for analysis.

- Diagnostic status (primary): Results were diagnostic, non-diagnostic (negative or variant of unknown significance (VUS) with inconsistent phenotype), uncertain (previously and/or not previously reported VUS identified and requires follow-up).
- Implications of WGS: confirmed a diagnosis within the differential diagnosis prior to testing, established a new diagnosis that was not previously suspected, produced a diagnosis unrelated to the clinical indication for testing [includes incidental findings and/or secondary findings], ruled out a suspected diagnosis/ diagnoses, eliminated the need for additional tests or evaluations, contributed to the overall diagnostic evaluation of this patient.
 - Diagnostic changes in management if diagnostic result (secondary): Referrals to New Healthcare Providers (inc. Specialty)
 - Disease-specific treatment or medication Changes (inc. Type and Detail)
 - Disease-specific screening (implemented new screening, screening implemented for suspected dx was justified)
 - Decisions on palliative care

- Participation in research study (Type)
- Family planning, counseling, or support (Type)

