5 STATISTICAL CONSIDERATIONS

5.1 Analysis Plan and Sample Size Determination

5.1.1 Analysis for Aim 1

The proportion of subjects who have a change in diagnosis status and the conditional proportion of subjects who were impacted by WGS will be calculated for the cohort, with 95% confidence intervals (95% CI). Individuals who were recruited to the previous (randomized crossover) version of this protocol will be included.

5.1.2 Analysis for Aim 2

The frequency and conditional proportion of subjects who received downstream changes in clinical management after a diagnostic result through WGS will be calculated for the cohort, with 95% confidence intervals (95% CI). The type of downstream clinical changes will be reported. Individuals who were recruited to the

previous (randomized crossover) version of this protocol and received a diagnosis through WGS will be included.

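### Does counting diagnoses made on reanalysis, with no index disclosure named and no Aim 1 cut-off, undermine the two estimates?

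*Combined protocol and SAP*

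**What the plan says.** Section 2.1 defines when the primary outcome is read: "Differences in diagnostic status will be measured at disclosure of initial results or disclosure of reanalyzed results". Two events can therefore establish a change in diagnostic status.

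The other timing rules use one event and do not say which it is when there are two:

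- Section 2.2 (Aim 2): "Differences in clinical care will be evaluated 1 year following disclosure of results".
- Section 3.1.2, in its heading: "Follow-Up Period (12 Months FOLLOWING REPORT".
- Section 3.2.1: "Study participation will last for 12 months following the disclosure of results".
- Section 4.1.1, on the source of clinical utility data: "medical record review 1 year prior to (retrospective) and 1 year following (prospective) disclosure of results".

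Section 5.1.1 plans a simple estimate for Aim 1, "The proportion of subjects who have a change in diagnosis status", with a 95% confidence interval. It includes subjects recruited under the earlier randomised crossover design. Section 5.1.2 does the same for "downstream changes in clinical management after a diagnostic result through WGS". Neither excludes diagnoses made on reanalysis, and neither sets a date after which a reanalysed result no longer counts. Section 5.1.4 commits only to reporting the proportion lost to follow-up.

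**The concern.** Take a subject whose first WGS report is not diagnostic and who is diagnosed when the data are reanalysed *m* months later. Section 4.1.1 uses one disclosure both to close the retrospective year and to open the prospective one, and this subject has two.

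- **Counted from the first report**, part of the prospective year is spent before the diagnosis exists. Changes made later in the year after diagnosis may be missed, which would lower the Aim 2 percentage. Section 5.1.4 would not show it, because the subject was never lost.
- **Counted from the diagnosing report**, part of the retrospective year falls after the first report. One category of first result in section 4.1.1 is "uncertain (previously and/or not previously reported VUS identified and requires follow-up", so care prompted by WGS could sit in the year treated as before. If participation were counted from the first report, the records needed would also run past its end.

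For Aim 1, a yield that includes reanalysis can only grow with time. The interim result in section 1.1 is given with its horizon (under 4 months), whereas section 5.1.1 gives none. Pooling the earlier recruits means that subjects may have had unequal time for reanalysis. At stake is whether two analysts working faithfully from the plan would reach the same percentages.

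**Working it through.** **The documents' own figure.** Section 1.1 reports a combined WGS and standard-of-care yield of 26/34. The components add up: 2 + 5 + 14 + 5 = 26. The proportion is 76.5% and the exact (Clopper-Pearson) interval is 58.8% to 89.3%, as stated. The concern does not rest on this figure. The achieved N = 80 in section 5.1.3.1 has no derivation to reproduce.

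**Window arithmetic (no assumed rates).** For a diagnosis *m* months after the first report, with *m* up to 12:

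- First-report anchor: records after diagnosis = 12 − *m*.
- Diagnosing-report anchor: records after diagnosis = 12, if participation is counted from the same disclosure; retrospective months after the first report = *m*; last month of records = 12 + *m*.

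| *m* | First-report anchor: months after diagnosis | Diagnosing-report anchor: months before / after diagnosis | Of the months before, those after the first report | Last record month |
|---|---|---|---|---|
| 3 | 9 | 12 / 12 | 3 | 15 |
| 6 | 6 | 12 / 12 | 6 | 18 |
| 9 | 3 | 12 / 12 | 9 | 21 |

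No single anchor gives both a year free of any WGS result and a full year after diagnosis. The diagnosing-report anchor does give a full year on each side of the diagnosis.

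**Which contrast Aim 2 asks for.** Section 2.2 restricts Aim 2 to subjects with a diagnostic result and to change that follows from the diagnosis; section 5.1.2 says the same. Care prompted by an uncertain first report is not such a change, so leaving it out of the Aim 2 count agrees with the definition. The plan also subtracts nothing between the two years: sections 4.1.1 and 4.1.2 have documented changes abstracted, and section 5.1.2 reports the proportion of diagnosed subjects with one.

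**Size under the unfavourable reading (first-report anchor).** The number *k* of reanalysis diagnoses is not in the documents. The following are assumptions:

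- First-report yield: WGS resolved (5 + 14)/(9 + 23) = 19/32 = 59.4% in section 1.1. That is not described as a first-report yield; it is a stand-in. Applied to 80 it gives about 48 diagnosed and 32 not.
- *k* = 2, 5 or 10 of those 32 (6%, 16% or about 30%).
- A 50% chance of a management change within 12 months, at constant rate.

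Change seen in the remaining months = 1 − 0.5^((12 − *m*)/12). For *m* = 6 this is 1 − 0.5^0.5 = 29.3%, a shortfall of 20.7 points per affected subject. For *m* = 9 it is 1 − 0.5^0.25 = 15.9%, a shortfall of 34.1 points. Multiply by the share of the Aim 2 denominator, *k*/(48 + *k*). Half-width = 1.96 × √(0.25/(48 + *k*)).

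| *k* | Share of Aim 2 | Aim 2 low by, *m* = 6 | Aim 2 low by, *m* = 9 | 95% half-width |
|---|---|---|---|---|
| 0 | 0% | 0 | 0 | – |
| 2 | 2/50 = 4.0% | 0.8 | 1.4 | 13.9 |
| 5 | 5/53 = 9.4% | 2.0 | 3.2 | 13.5 |
| 10 | 10/58 = 17.2% | 3.6 | 5.9 | 12.9 |

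Under the diagnosing-report anchor, with participation counted from the same disclosure, the shortfall is zero in every row.

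**Aim 1.** Each subject added by reanalysis is 1/80 = 1.25 points, so *k* = 2, 5 or 10 adds 2.5, 6.25 or 12.5 points. These are not errors: section 2.1 makes such subjects part of the outcome. What is unstated is the date at which counting stops.

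**The case for a change.** The strongest case for acting is that the text does not name the index disclosure, so the reading above is an inference. An abstractor could take the first report as the anchor everywhere and give some diagnosed subjects a short year that no planned table reveals. Section 2 asks broadly whether WGS changes management, and section 4.1.1 lists effects that need no diagnosis, such as ruling out a suspected disorder or removing the need for further tests; on that broad question, a baseline year containing a first WGS report is not clean. The Aim 1 horizon is also a separate gap, untouched by the choice of anchor, and the pooled recruits may have had different time for reanalysis.

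Part of this stands. The index date is unnamed, and no reanalysis cut-off is written down. The 12-month participation period might serve as an implicit limit, but its own starting point has the same ambiguity.

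The rest does not carry. The broad wording in section 2 is made specific in sections 2.2 and 5.1.2, which tie Aim 2 to a diagnostic result. Tighter rules are not clearly better either. Fixing participation at 12 months from the first report while starting the Aim 2 year at the diagnosing report would give every subject diagnosed on reanalysis a short year, since *m* + 12 ≤ 12 only when *m* = 0; the present wording of section 3.2.1 at least allows participation to run from the diagnosing disclosure. Counting reanalyses only up to 12 months would narrow the primary outcome on no basis in the documents, after N = 80 had already been reached.

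**Conclusion.** This is a gap that analysts fill sensibly, and no change to the plan follows. For a subject diagnosed on reanalysis, the disclosure that matters for Aim 2 is the one that delivered the diagnosis. With participation read from the same disclosure, the subject has a full year on each side of it. For Aim 1, a reader needs the data cut-off and would like first-report and reanalysis diagnoses counted separately. Both are ordinary reporting items and can be produced from the disclosure dates without altering the analysis.

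The effect is small even on the less natural reading. For two or five reanalysis diagnoses at month 6, Aim 2 would be 0.8 or 2.0 points low. Ten at month 9 would make it 5.9 points, still less than half of the 12.9-point half-width. These figures rest on an assumed first-report yield of 48/80, an assumed 50% change proportion, a constant rate and assumed counts and timings; the documents give none of them, and the number affected may be zero. The Aim 1 additions can be larger, at 1.25 points per subject, but they belong to the outcome as section 2.1 defines it and are not bias.

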2.2 Secondary Objective (or Aim 2)

Estimate the percentage of cases that experience a significant change in downstream clinical management as a direct consequence of a diagnosis through whole genome sequencing (subjects with a diagnostic result).

The secondary objective of this study is to evaluate changes in clinical care in subjects who received a diagnosis through WGS. Differences in clinical care will be evaluated 1 year following disclosure of results.

3 INVESTIGATIONAL PLAN

3.1 General Schema of Study Design

This is an observational study of subjects who are expected to receive CLIA-certified whole genome sequencing as part of their clinical care.

3.1.1 Screening Procedures

Candidates with a suspected leukodystrophy or other suspected genetic disorder affecting the white matter of the brain will be provided with information about the study by a qualified member of the study team. Interested candidates will be invited to enroll in CHOP IRB 14-011236 to facilitate collection and review of medical records. At a minimum, these records must include a copy of the most recent neurologic exam and brain MRI. Additional notes, reports, test results, imaging studies, etc. will be requested if available.

Candidates who meet basic eligibility requirements will then be independently reviewed by [name], MD, a pediatric neurologist at McGill University with significant expertise in MRI pattern recognition. [name] may receive abstract clinical summaries, as well as radiology studies that have been coded with a unique study identifier generated by the CHOP study team. [name] will not be able to link these study identifiers to PHI.

MRIs will be analyzed according to a publicly available non-computational algorithm accessible to even non-expert child neurologists and geneticists⁴⁶. Candidates may be enrolled irrespective of the clinician's presumptive diagnosis (even if the clinician feels there is an unambiguous diagnosis based on MRI and initial clinical assessment), as long as no confirmatory testing has been performed. Each candidate's MRIs must be reviewed by at least two of the four experts. If necessary, candidates will be reclassified with respect to their pre-test diagnostic probabilities.

